5.4 PROCEDURES FOR ELICITING, RECORDING, AND REPORTING ADVERSE EVENTS

5.4.1 ELICITING ADVERSE EVENTS

A consistent methodology for eliciting AEs at all subject evaluation time points should be adopted. Examples of non-directive questions include:

- “How have you felt since your last clinical visit?”
- “Have you had any new or changed health problems since you were last here?”

5.4.2 SPECIFIC INSTRUCTIONS FOR RECORDING ADVERSE EVENTS

Investigators should use correct medical terminology/concepts when reporting AEs or SAEs. Avoid colloquialisms and abbreviations.

5.4.2.1 Diagnosis vs. Signs and Symptoms

If known at the time of reporting, a diagnosis should be reported rather than individual signs and symptoms (e.g., record only liver failure or hepatitis rather than jaundice, asterixis, and elevated transaminases). However, if a constellation of signs and/or symptoms cannot be medically characterized as a single diagnosis or syndrome at the time of reporting, it is acceptable to report the information that is currently available. If a diagnosis is subsequently established, it should be reported as follow-up information.

5.4.2.2 Deaths

All deaths that occur during the protocol-specified AE reporting period (see Section I), regardless of attribution, will be reported to the appropriate parties. When recording a death, the event or condition that caused or contributed to the fatal outcome should be reported as the single medical concept. If the cause of death is unknown and cannot be ascertained at the time of reporting, report "Unexplained Death".

5.4.2.3 Preexisting Medical Conditions

A preexisting medical condition is one that is present at the start of the study. Such conditions should be reported as medical and surgical history. A preexisting medical condition should be re-assessed throughout the trial and reported as an AE or SAE only if the frequency, severity, or character of the condition worsens during the study. When reporting such events, it is important to convey the concept that the preexisting condition has changed by including applicable descriptors (e.g., "more frequent headaches").

5.4.2.4 Hospitalizations for Medical or Surgical Procedures

Any AE that results in hospitalization or prolonged hospitalization should be documented and reported as an SAE. If a subject is hospitalized to undergo a medical or surgical procedure as a result of an AE, the event responsible for the procedure, not the procedure itself, should be reported as the SAE. For example, if a subject is hospitalized to undergo coronary bypass surgery, record the heart condition that necessitated the bypass as the SAE.

Hospitalizations for the following reasons do not require reporting:

- Hospitalization or prolonged hospitalization required to allow efficacy measurement for the study or
- Hospitalization or prolonged hospitalization for scheduled therapy of the target disease of the study

5.4.2.5 Assessment of Severity of Adverse Events

The adverse event severity grading scale for the NCI CTCAE v 5.0 Update current versions) will be used for assessing adverse event severity. Below Table should be used for assessing severity for adverse events that are not specifically listed in the NCI CTCAE.

Adverse Event Severity Grading Scale for Events Not Specifically Listed in NCI CTCAE

Grade	Severity
1	Mild; asymptomatic or mild symptoms; clinical or diagnostic observations only; or intervention not indicated
2	Moderate; minimal, local, or non-invasive intervention indicated; or limiting age-appropriate instrumental activities of daily living ^a
3	Severe or medically significant, but not immediately life-threatening; hospitalization or prolongation of hospitalization indicated; disabling; or limiting self-care activities of daily living ^{b,c}
4	Life-threatening consequences or urgent intervention indicated ^d
5	Death related to adverse event ^d

NCI CTCAE = National Cancer Institute Common Terminology Criteria for Adverse Events.

Note: Based on the most recent version of NCI CTCAE v 5.0 which can be found at: http://ctep.cancer.gov/protocolDevelopment/electronic_applications/ctc.htm

- a. Instrumental activities of daily living refer to preparing meals, shopping for groceries or clothes, using the telephone, managing money, etc.
- b. Examples of self-care activities of daily living include bathing, dressing and undressing, feeding oneself, using the toilet, and taking medications, as performed by patients who are not bedridden.
- c. If an event is assessed as a "significant medical event," it must be reported as a serious adverse event
- d. Grade 4 and 5 events must be reported as serious adverse events

5.4.3 PREGNANCY

If a female subject becomes pregnant while receiving the study drug or within *90 days* after the last dose of study drug, or if the female partner of a male study subject becomes pregnant while the study subject is receiving the study drug or within *90 days* after the last dose of study drug, a report should be completed and expeditiously submitted to Genentech, Inc. Follow-up to obtain the outcome of the pregnancy should also occur. Abortion, whether accidental, therapeutic, or spontaneous, should always be classified as serious, and expeditiously reported as an SAE. Similarly, any congenital anomaly/birth defect in a child born to a female subject exposed to the study drug should be reported as an SAE.

5.4.4 AEs OF SOCIAL INTERESTS (AESIs)

AESIs are a subset of Events to Monitor (EtMs) of scientific and medical concern specific to the product, for which ongoing monitoring and rapid communication by the Investigator to the Sponsor is required. Such an event might require further investigation in order to characterize and understand it. Depending on the nature of the event, rapid communication by the trial Sponsor to other parties (e.g., Regulatory Authorities) may also be warranted.

Adverse events of special interest for this study include the following:

- Cases of potential drug-induced liver injury that include an elevated ALT or AST in combination with either an elevated bilirubin or clinical jaundice, as defined by Hy's law:
- Treatment-emergent ALT or AST $> 3 \times \text{ULN}$ in combination with total bilirubin $> 2 \times \text{ULN}$
- Treatment-emergent ALT or AST $> 3 \times \text{ULN}$ in combination with clinical jaundice
- Data related to a suspected transmission of an infectious agent by the study drug (STIAMP), as defined below:
 - Any organism, virus, or infectious particle (e.g., prion protein transmitting transmissible spongiform encephalopathy), pathogenic or non-pathogenic, is considered an infectious agent. A transmission of an infectious agent may be suspected from clinical symptoms or laboratory findings that indicate an infection in a patient exposed to a medicinal product. This term applies only when a contamination of the study drug is suspected.

5.4.5 OTHER SPECIAL SITUATIONS REPORTS

The following other Special Situations Reports should be collected even in the absence of an Adverse Event and transmitted to Genentech:

- Data related to the Product usage during breastfeeding
- Data related to overdose, abuse, misuse or medication error (including potentially exposed or intercepted medication errors)
- In addition, reasonable attempts should be made to obtain and submit the age or age group of the patient, in order to be able to identify potential safety signals specific to a particular population.

5.4.7 POST-STUDY ADVERSE EVENTS

The investigator should expeditiously report any SAE occurring after a subject has completed or discontinued study participation if attributed to prior baloxavir exposure. If the investigator should become aware of the development of cancer or a congenital anomaly in a subsequently conceived offspring of a female subject [add if applicable-including pregnancy occurring in the partner of a male study subject] who participated in the study, this should be reported as an SAE adequately to Genentech drug Safety during follow up period.

5.4.8 EXCHANGE OF SINGLE CASE REPORTS

Weill Cornell Medical College will be responsible for collecting all protocol-defined Adverse Events (AEs)/Serious Adverse Events (SAEs), pregnancy reports (including pregnancy occurring in the partner of a male study subject), other Special Situation reports, AESIs and Product Complaints with an AE where the patient has been exposed to the Product. *Weill Cornell Medical College* will submit SAEs, AESIs, Special Situations, and any pregnancy to Genentech using the MedWatch Form. Transmission of these reports (initial and follow-up) will be either electronically via email or by fax and within the timelines specified below:

[contact]

Email: [contact]

All Product Complaints without an AE should call via:
PC [contact] (M-F: 5 am to 5 pm PST)

Transmission of these reports (initial and follow-up) will be either electronically or by fax and within the timelines specified below:

Type of Report	Timelines
Serious Adverse Events (related and not related to the Product)	
Special Situation Reports (With or without AE and pregnancy)	30 calendar days from awareness date
Product Complaints (With or without AE)	
AESI	

5.4.9 CASE TRANSMISSION VERIFICATION OF SINGLE CASE REPORTS

- The parties will verify that all single case reports have been adequately received by Genentech by emailing Genentech a Quarterly line-listing documenting single case reports sent to Genentech in the preceding time period.
- The periodic line-listing will be exchanged within seven (7) calendar days of the end of the agreed time period. Confirmation of receipt should be received within the time period mutually agreed upon.
- If discrepancies are identified, the Sponsor and Genentech will cooperate in resolving the discrepancies. The responsible individuals for each party shall handle the matter on a case-by-case basis until satisfactory resolution. The sponsor shall receive reconciliation guidance documents within the 'Activation Package'.
- Following Case Transmission Verification, single case reports which have not been received by Genentech shall be forwarded to Genentech within five (5) calendar days from request by Genentech.

At the end of the study, a final cumulative Case Transmission Verification report will be sent to Genentech: [contact]

MEDWATCH 3500a REPORTING GUIDELINES

In addition to completing appropriate patient demographic (Section A) and suspect medication information (Section C & D), the report should include the following information within the Event Description (Section B.5) of the MedWatch 3500A form:

- Protocol number and title description
- Description of event, severity, treatment, and outcome if known
- Supportive laboratory results and diagnostics (Section B.6)
- Investigator's assessment of the relationship of the adverse event to each investigational product and suspect medication

Follow-Up Information

- Additional information may be added to a previously submitted report by any of the following methods:

- Adding to the original MedWatch 3500A report and submitting it as follow-up
- Adding supplemental summary information and submitting it as follow-up with the original MedWatch 3500A form
- Summarizing new information and faxing it with a cover letter including patient identifiers (i.e. D.O.B. initial, patient number), protocol description and number, if assigned, brief adverse event description, and notation that additional or follow-up information is being submitted (The patient identifiers are important so that the new information is added to the correct initial report)

MedWatch 3500A (Mandatory Reporting) form is available at:

<https://www.fda.gov/media/69876/download>

5.4.10 REPORTING TO REGULATORY AUTHORITIES, ETHICS COMMITTEES AND INVESTIGATORS

Genentech as the Marketing Authorization Holder will be responsible for the reporting of individual case safety reports from the study to the regulatory authority in compliance with applicable regulations. WCMC, as the Sponsor of the Study, will be responsible for the expedited reporting of safety reports originating from the study to the EMA through Eudravigilance Clinical Trial Module (EVCTM), where applicable.

WCMC will be responsible for the expedited reporting of safety reports originating from the Study to the Ethics Committees and Institutional Review Boards (IRB), where applicable.

WCMC as the Sponsor of the Study, will be responsible for the preparation of six-monthly Suspected Unexpected Serious Adverse Reaction (SUSAR) reports and their submission to Investigators, Regulatory Authorities and the Institutional Review Board/Independent Ethics Committee (IRB/IEC), where applicable
WCMC will be responsible for the distribution of safety information to its own investigators, where relevant, in accordance with local regulations.

5.4.11 AGGREGATED REPORTS

Development Safety Update Reports

WCMC as the Sponsor of the Study, will be responsible for the preparation of their own Development Safety Update Report (DSUR) for the Study and for the submission of the report to the regulatory authorities and Ethics Committees of the concerned Member States, where applicable. WCMC agrees to share a copy of their own DSUR with Genentech as soon as reasonably possible after completion.

Genentech agrees to forward to WCMC an executive summary of the Genentech DSUR upon request. Furthermore, Genentech agrees that WCMC may cross-reference the executive summary of the Genentech DSUR, as applicable.

Other Reports

WCMC will forward a copy of the Publication to Genentech upon completion of the Study.

5.4.12 STUDY CLOSE-OUT

Any study report submitted to the FDA by the Sponsor-Investigator should be copied to Genentech. This includes all IND annual reports and the Clinical Study Report (final study report). Additionally, any literature articles that are a result of the study should be sent to Genentech. Copies of such reports should be mailed to the assigned

Clinical Operations contact for the study:

[name]
[contact]

And to Genentech Drug Safety CTV oversight mail box at: [contact]

Queries

Queries related to the Study will be answered by WCMC. However, responses to all safety queries from regulatory authorities or for publications will be discussed and coordinated between the Parties. The Parties agree that Genentech shall have the final say and control over safety queries relating to the Product. WCMC agrees that it shall not answer such queries from regulatory authorities and other sources relating to the Product independently but shall redirect such queries to Genentech.

Both Parties will use all reasonable effort to ensure that deadlines for responses to urgent requests for information or review of data are met. The Parties will clearly indicate on the request the reason for urgency and the date by which a response is required.

Signal Management and Risk Management

Genentech is responsible for safety signal management (signal detection and/or evaluation) for their own Product. However, it is agreed that **WCMC**, as Sponsor of the Study, will be primarily responsible for assessment of the benefit-risk balance of the Study.

If **WCMC** issues a safety communication relevant for Genentech (i.e., a safety issue that notably impacts the benefit-risk balance of the Study and / or triggers any changes to the Study) this will be sent to Roche within five (5) business days of its internal approval.

As needed, Genentech will reasonably assist **WCMC** with signal and risk management activities related to the Product within the Study.

Genentech will also provide **WCMC** with any new relevant information that may modify or supplement known data regarding the Product (e.g., relevant Dear Investigator Letter).

Compliance with Pharmacovigilance Agreement / Audit

The Parties shall follow their own procedures for adherence to AE reporting timelines.

Each Party shall monitor and, as applicable, request feedback from the other Party regarding AE report timeliness in accordance with its own procedures. The Parties agree to provide written responses in a timely manner to inquiries from the other Party regarding AE reports received outside the agreed upon Agreement timelines. If there is any detection of trends of increasing or persistent non-compliance to transmission timelines stipulated in this Agreement, both Parties agree to conduct ad hoc or institute a regular joint meeting to address the issue.

In case of concerns related to non-compliance of processes, other than exchange timelines, with this Agreement, the Parties will jointly discuss and collaborate on clarifying and resolving the issues causing non-compliance. Every effort will be made by the non-compliant Party to solve the non-compliance issues and inform the other Party of the corrective and preventative actions taken.

Upon justified request, given sufficient notice of no less than sixty (60) calendar days, an audit under the provisions of this Agreement can be requested by either Party. The Parties will then discuss and agree in good faith upon the audit scope, agenda and execution of the audit. The requesting Party will bear the cost of the audit.

STATISTICAL CONSIDERATIONS

The study plans to enroll a total of 30 allogeneic bone marrow transplant patients who will be randomized at 1:1 to the two study arms. The primary endpoint data will be analyzed on the basis of a modified intention-to-treat (ITT) principle for patients with viral loads measurements at both the baseline and day 10.

For the first co-primary objective, the effects of the study drugs will be evaluated separately for each study arm by estimating the change in viral RNA loads from baseline (day1) at the end of treatment (day10) as measured by qRT-PCR. Summary statistics including mean, standard deviation, median and range of the primary endpoints will be calculated for each arm. Difference in log transformed viral RNA loads measured at the end of treatment and at baseline will be evaluated using paired t-test or the Wilcoxon signed rank test for each arm separately. For the second co-primary endpoint, efficacy of the baloxavir + oseltamivir will be assessed through estimating the differences in the magnitude of change in viral RNA loads from baseline at the end of treatment between the two treatment arms along with the 95% confidence intervals. Given the pilot nature of the study, the sample size is primarily based on feasibility and logistic considerations. However, based on prior studies [ref: Infect Dis Ther (2019) 8:613–626], the expected baseline viral RNA loads for the immunocompromised patients would be around $6.5 \log_{10} \text{vp/mL}$ with standard deviation around $3 \log_{10} \text{vp/mL}$. With 15 patients in a study arm, we would have 80% power to detect a difference of $2.33 \log_{10} \text{vp/mL}$ in viral RNA loads at the end of treatment vs. at the baseline assuming similar level of standard deviation at the end of treatment with a two-sided 0.05 significance level using a paired t-test. We expect to have adequate power to detect this level of change for both the study arms since prior study has observed a decrease of at least $3 \log_{10} \text{vp/mL}$ with Oseltamivir alone in immune compromised patients [ref: Infect Dis Ther (2019) 8:613–626]. For the second co-primary endpoint, i.e., the between arm differences in change in viral loads, 15 patients per arm will allow 80% power to detect effects size as small as 1.1 standard deviation at a two-sided 0.05 significance level. It is likely the study is under-powered but is expected to generate meaningful preliminary efficacy data [Machin, D, Campbell, M.J., Tan, S.B, Tan, S.H. 2018. 'Sample Sizes for Clinical, Laboratory and Epidemiology Studies, Fourth Edition', Chapter 16. John Wiley and Sons. Hoboken, New Jersey.].

For secondary viral loads related endpoints, summary statistics in terms of mean, standard deviation, median and range will be calculated for each arm at each time points among patients with relevant measurements. Longitudinal analyses using mixed effects repeated measures will be used to model the mean viral loads overall time. Contrasts of interest including between arm differences will be explored using simultaneous tests of general linear hypotheses. If normality is a concern, log-transformed and standardized viral load data will be used. Longitudinal analysis will be carried out among patients with at least one relevant viral load measurement. Kaplan-Meier estimates will be generated for time to events endpoints such as time to Improvement of Individual Influenza Symptoms, the time to viral clearance and time to return to preinfluenza health status for each study arm. Between study arm difference in these endpoints will be explored using the generalized Wilcoxon test.

Categorical data such as the occurrence of treatment-emergent variants of neuraminidase and polymerase by direct next-generation sequencing and AE's will be summarized in terms of counts and proportions separately for each arm.

Between arm difference in the categorical variable will be explored using Fisher's exact test. The study is likely will not have adequate power to detect between arm differences and all the between arms comparisons are considered exploratory. Summary statistics generated for study endpoints for each arm will provide useful information for planning future studies.

The power calculations were performed using PASS 15 Power Analysis and Sample Size Software (2017). NCSS, LLC. Kaysville, Utah, USA, ncss.com/software/pass. All comparisons will be two-tailed, with a significance level at 0.05 and 95% confidence intervals will also be reported. All analyses will be performed in SAS Version 9.4 (2019), SAS Institute, Inc., Cary, NC; and R Version 4.0.4 (2021).

Note: The statistical considerations section was written by [name], MS, and revised by [name], in the Division of Biostatistics, Department of Population Health Sciences, Weill Cornell Medicine.

Influenza sequence analysis will be performed by [name], Director of Systems Genomics Section at the Laboratory of Parasitic Diseases of NIAID/NIH and expert in Influenza evolution.

No interim analysis is planned for this study

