2. OBJECTIVES AND ENDPOINTS

2.1 PRIMARY OBJECTIVE

The primary objective is to evaluate the efficacy of both the combination therapy of baloxavir with oseltamivir and that of oseltamivir plus placebo in SCT patients with influenza as measured by changes in influenza viral RNA loads at day 10 from baseline (day 1) and compare between arm differences in decline of viral load

The co-primary efficacy endpoints are:

- Change of influenza viral RNA loads from baseline (day 1) at the end of treatment (day 10) as measured by quantitative real time polymerase chain reaction (qRT-PCR, nucleic acid).
- Between-treatment-arm difference in the change of influenza viral RNA loads from baseline (day 1) at the end of treatment (day 10) as assessed by quantitative real time polymerase chain reaction as measured by (qRT-PCR, nucleic acid) and by Influenza plaque assay (replicating virus).

The secondary efficacy endpoints are:

1. **Change of influenza viral RNA load from baseline (day 1) at day 4 and day 7 and 10** as measured by quantitative real time polymerase chain reaction (qRT-PCR, nucleic acid) in each treatment arm.
2. **Difference in change of influenza viral loads from baseline (day 1) at day 4, 7 and 10 between the two treatment arms** as measured by quantitative real time polymerase chain reaction (qRT-PCR, nucleic acid)
3. **Change of influenza viral loads from baseline (day 1) at day 4, 7 and 10** as measured by Influenza plaque assay (replicating virus) in each treatment arm.
4. **Difference in change of influenza viral loads from baseline (day 1) at day 4, 7 and 10 between the two treatment arms** as measured by Influenza plaque assay (replicating virus).
5. **Time to Improvement of Individual Influenza Symptoms** [Time Frame: From Day 1 pre-treatment up to Day 30] defined as the time from the initiation of the study treatment to the improvement of influenza symptoms as assessed by patient-reported outcome measures on a single scale as specified in section 4.5.7. Time to improvement of symptoms is defined as the time from the start of treatment to the time when each of the influenza symptoms will be alleviated, maintained, or improved, for a duration of at least 24 hours.

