3. STUDY DESIGN

3.1 DESCRIPTION OF THE STUDY

This is a randomized double-blind placebo-controlled pilot study of the efficacy and safety of baloxavir in combination with oseltamivir (SOC) for the treatment of influenza in allogeneic stem cell transplant patients.

30 SCT recipients with influenza will take part in the study. Participants will be randomly assigned (1:1) to either baloxavir + oseltamivir or baloxavir-matched placebo +oseltamivir. Randomization will be performed by research pharmacy using an interactive web randomizer. Before randomization, patients will be stratified by hospitalization status (yes or no), influenza type A (yes or no).

Patients in the baloxavir combination arm will receive weight-adjusted baloxavir (40 mg for patients weighing <80 kg and 80 mg for those weighing \geq 80 kg) at baseline and at day 4 and day 7. They will also receive oseltamivir 75 mg twice daily for 10 days.

Patients in the baloxavir-matched placebo + oseltamivir arm will receive baloxavir-matched placebo at baseline and at day 4 and day 7 and oseltamivir 75 mg twice daily for 10 days.

Nasopharyngeal swabs will be collected on days 1 (at diagnosis, pre-meds), 2, (optional visit), 4, 7 and 10 for viral quantitation and viral sequencing. Influenza virus polymerase and neuraminidase sequencing will be also performed in all patients. Patients will have follow-up visits day 15 (+/- 2 days) and day 30 (+/- 2 days, EOT). Patients who will not clear the virus by day 10 will perform additional NP swabs at these visits.

Paracetamol (acetaminophen; maximum 3000 mg per day) or NSAIDS can be given for severe discomfort or fever. No other antiviral drugs for the treatment of influenza, will be permitted, except antibiotics for the treatment of suspected bacterial infections.

For the first 10 days, patients will receive a daily call from one member of the study team to review symptoms and severity scale.

To assess the **time to improvement of individual influenza symptoms** (with modification for preexisting symptoms), participants will be given a diary to self-assess the severity of seven influenza-associated symptoms on a four-point scale. To evaluate patient-reported **time to return to pre-illness health status**, patients will also rate **daily the interference of influenza symptoms in daily activities** on a 5-point severity scale.

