4. MATERIALS AND METHODS

4.1 PATIENTS

Approximately 30 patients with allogeneic bone marrow transplant will be enrolled in this study.

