4.1.1 INCLUSION CRITERIA

Patient must meet the following criteria for study entry:

- Adult patients: Signed informed consent by any patient capable of giving consent, or, where the patient is not capable of giving consent, by his or her legal/authorized representative
- Age \geq 18 years at the time of signing the Informed Consent Form/Accent Form
- Ability to comply with the study protocol, in the investigator's judgment
- Be defined as immunocompromised*, as defined by:
 1. Have received allogeneic bone marrow transplant, or
 2. Is currently receiving treatment with chemotherapy and/or CAR-T cell therapy for hematologic malignancies (e.g., leukemia, myeloma, lymphoma), or

- 3. Received treatment with chemotherapy and/or CAR-T cell therapy for hematologic malignancies (e.g., leukemia, myeloma, lymphoma) within the past 1 year.
- Tested positive for influenza infection after the onset of symptoms using a polymerase chain reaction (PCR)-based diagnostic assay.
- Presence of (a) fever ($\geq 38.0^{\circ}\text{C}$ per tympanic or rectal thermometer; $\geq 37.5^{\circ}\text{C}$ per axillary, oral or forehead/temporal thermometer) or (b) any influenza symptoms (cough, sore throat, nasal congestion, headache, feverishness or chills, muscle or joint pain, fatigue).
- The time interval between the diagnosis of influenza and the pre-dose examinations is 48 hours or less.
- For women of childbearing potential: Agreement to remain abstinent (refrain from heterosexual intercourse):

Women must remain abstinent or use contraceptive methods with a failure rate of $< 1\%$ per year during the treatment period and for 28 days after the last dose of study treatment.

Hormonal contraceptive methods must be supplemented by a barrier method.

A woman is considered to be of childbearing potential if she is postmenarcheal, has not reached a postmenopausal state (≥ 12 continuous months of amenorrhea with no identified cause other than menopause), and has not undergone surgical sterilization (removal of ovaries and/or uterus).

Examples of contraceptive methods with a failure rate of $< 1\%$ per year include bilateral tubal ligation, male sterilization, hormonal contraceptives that inhibit ovulation, hormone-releasing intrauterine devices, and copper intrauterine devices.

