The reliability of sexual abstinence should be evaluated in relation to the duration of the clinical trial and the preferred and usual lifestyle of the patient. Periodic abstinence (e.g., calendar, ovulation, symptothermal, or postovulation methods) and withdrawal are not acceptable methods of contraception.

*This study will enroll a minimum of 10 patients who have received allogeneic bone marrow transplant.

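### The objective, design and sample size name transplant recipients, but eligibility needs no transplant and assures only 10 allogeneic recipients of 30, so a pooled result may be credited to the wrong population

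*Combined protocol and SAP*

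**What the plan says.** Five places describe the enrolled population as transplant recipients:

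- **Section 1.3 (rationale)** states that SCT recipients with influenza will be randomized.
- **Section 2.1 (primary objective)** evaluates both regimens "in SCT patients with influenza as measured by changes in influenza viral RNA loads at day 10".
- **Section 3.1 (design)** describes a trial "for the treatment of influenza in allogeneic stem cell transplant patients" and says "30 SCT recipients with influenza will take part in the study".
- **Section 4.1** says "Approximately 30 patients with allogeneic bone marrow transplant will be enrolled in this study".
- **Statistical Considerations** opens with "The study plans to enroll a total of 30 allogeneic bone marrow transplant patients".

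Sections 3.1, 4.1 and Statistical Considerations say allogeneic. Sections 1.3 and 2.1 say only SCT. Sections 3.3.1, 3.3.3 and 5.2 also use SCT wording, though they do not state who is enrolled.

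Section 4.1.1 defines eligibility differently. A patient qualifies as immunocompromised by any one of three routes joined by *or*. The first is an allogeneic transplant. The second is "Is currently receiving treatment with chemotherapy and/or CAR-T cell therapy for hematologic malignancies". The third is "Received treatment with chemotherapy and/or CAR-T cell therapy for hematologic malignancies", within the past year. The footnote to that section adds: "This study will enroll a minimum of 10 patients who have received allogeneic bone marrow transplant".

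Randomization is stratified by hospitalization and influenza type A only (Sections 3.1 and 4.3). The primary analysis uses patients with viral loads at both baseline and day 10, and Statistical Considerations describes every analysis by arm, with none by transplant status.

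**The concern.** Section 4.1 and Section 4.1.1 cannot both govern. A floor of 10 allogeneic recipients has a purpose only if other patients may enrol, yet Section 4.1 and Statistical Considerations plan for essentially all 30 to be allogeneic.

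If sites enrol by the inclusion criteria and the analysis is run as described, patients of all three routes are pooled and the estimate is read against an objective worded for SCT patients. Those patients could be as few as one third of the sample, if none of the others has had a transplant. Routes 2 and 3 neither require nor exclude an autologous transplant, so even the SCT share is unknown unless the protocol says whether SCT means allogeneic only. The floor also applies to enrolment: recipients without both viral loads leave the primary analysis, so fewer than 10 could contribute to it.

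The plan says its per-arm summaries are meant to help plan later studies. That use depends on knowing whose data they are, for the within-arm co-primary endpoint as well as for the between-arm one.

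**Working it through.** **1. The plan's own figures.** The inputs, all from Statistical Considerations, are 15 per arm, SD about 3 log10, two-sided alpha 0.05, a within-arm change of 2.33 log10 and a between-arm effect of 1.1 SD. Power comes from the noncentral t distribution.

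- Within arm: noncentrality = (2.33/3) × √15 = 3.01, df 14, power 79.9%. This takes the SD of the *change* as 3. Since SD of change = 3 × √(2(1 − ρ)), it implies a baseline to day-10 correlation ρ of 0.5, which the plan does not state. At ρ = 0 the SD is 4.24 and power is 51%.
- Between arms: noncentrality = 1.1/√(1/15 + 1/15) = 3.01, df 28, power 82.8%. The effect detectable at 80% power is 1.06 SD, which rounds to the stated 1.1.

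The figures reproduce for 15 analysed patients per arm, the within-arm one on that assumed correlation. The question is which population those 30 represent.

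**2. Composition allowed by Section 4.1.1.** Maximum non-allogeneic = 30 − 10 = 20, or 20/30 = 67%. The minimum is 0, because all 30 could be allogeneic.

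**3. Attribution.** Let f be the allogeneic share, and let D be the absolute difference in true effect between allogeneic and other patients. In expectation,

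pooled effect = f × (allogeneic effect) + (1 − f) × (effect in others),

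so the pooled effect misses the allogeneic effect by (1 − f) × D. The documents give no value for D; those below are assumptions.

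| Allogeneic of 30 | Error | D = 0.5 log10 | D = 1 log10 | D = 2 log10 |
|---|---|---|---|---|
| 10 | 0.67 D | 0.33 | 0.67 | 1.33 |
| 20 | 0.33 D | 0.17 | 0.33 | 0.67 |
| 30 | 0 | 0 | 0 | 0 |

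The error can go either way. With an assumed benefit of 1.5 log10 in allogeneic recipients and 0 in the others, the pooled value at 10 of 30 is 1.5 × 1/3 = 0.5. With the benefits reversed it is 1.5 × 2/3 = 1.0, although allogeneic recipients gain nothing.

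**4. What the assured 10 could show on their own.** The 95% half-width in SD units is t(0.975, n1 + n2 − 2) × √(1/n1 + 1/n2). For 5/5 it is 2.306 × √0.4 = 1.46.

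| Split between arms | Power at 1.1 SD | 95% CI half-width |
|---|---|---|
| 15/15 (plan) | 83% | 0.75 SD |
| 5/5 | 33.5% | 1.46 SD |
| 4/6 | 32% | 1.49 SD |
| 3/7 | 29% | 1.59 SD |
| 2/8 | 23% | 1.82 SD |

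Within one arm, 5 recipients and an SD of change of 3 give 27% power for 2.33 log10.

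An even split is not assured, because transplant status is not a stratum. With 10 recipients among 30 patients allocated 15/15, ignoring the two actual strata, the hypergeometric probability of exactly 5/5 is 0.300. The probability of 3/7 or more extreme is 0.245.

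**The case against.** The strongest reply is that this is a feasibility-sized pilot. The plan itself says that it is probably under-powered and that between-arm comparisons are exploratory. No document suggests that the effect differs by transplant status, so D is hypothetical. Even the largest assumed error, 1.33 log10, lies inside the pooled 95% half-width of about 0.748 × 3 = 2.24 log10 (SD of change taken as 3). The sample-size inputs come from immunocompromised patients, and Section 1.3 mentions such patients in general terms. Section 3.3.2, the stated rationale for the patient population, refers only to influenza A or B. All 30 could turn out to be allogeneic. Baseline history under Section 4.5.2 would in any case let the report describe the actual mix.

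Much of this stands. Power is not the complaint, the 15-per-arm figures can fairly describe a mixed cohort, and D is an assumption. Leaving transplant status out of the stratification is defensible with 30 patients and two factors already. A summary of about 10 recipients will also be imprecise.

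None of it reconciles the text. General mentions of immunocompromised hosts do not name a non-transplant group as enrolled, whereas Section 1.3 says who will be randomized and that is SCT recipients. A wide interval does not make it acceptable to attach the estimate to the wrong group. Describing the mix afterwards would leave the objective and the stated sample still naming transplant recipients.

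**Conclusion.** The concern holds. As written, the plan states two populations. Following the inclusion criteria can produce a cohort up to two-thirds non-allogeneic, with its pooled result reported against an SCT objective. The composition limit follows directly from the text at the planned total of 30. The attribution error of up to 0.67 D rests on an assumed D and on exactly 10 allogeneic recipients among 30 analysed; it vanishes if all 30 are allogeneic or if D is zero. The subgroup power and interval widths only illustrate how little the assured 10 could show alone. This needs correction because the identity of the study population underlies the objective, the sample-size statement and any conclusion.

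**What to change.** The sponsor-investigator should choose the population and make Sections 1.3, 2.1, 3.1, 4.1, 4.1.1 and Statistical Considerations name it consistently. The SCT wording in Sections 3.3.1, 3.3.3 and 5.2 should be aligned, and the protocol should state whether SCT means allogeneic only.

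- **If the broad criteria stay:** restate the population in the rationale, objective, design, Section 4.1 and statistical section. Attach the 15-per-arm power to that mixed population only. Add a descriptive summary of the allogeneic recipients, within arm and between arms, with 95% confidence intervals, and let any transplant-specific statement rest on that summary and its wide interval.
- **If eligibility is limited to allogeneic recipients:** revise Section 4.1.1 and its footnote. The population wording and sample size in Statistical Considerations can then stand.

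The first option costs wording changes and one summary, using a status already established at the eligibility check, with no extra patients. Its downside is a less favourable stated precision for transplant recipients. The second option's cost is slower accrual.
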